7.5.1 Overall Response Rate

The overall response rate (ORR) is defined as proportion of subjects for whom the best overall confirmed response is stringent complete response (sCR), complete response (CR), very good partial response (vGPR), or partial response (PR) as defined by International Myeloma Working Group Uniform Response Criteria (IMWG-URC). An estimate of the ORR and its 1-sided 95% exact binomial confidence interval for each of the recommended dose groups will be determined. Additionally, the ORR along with the

associated 2-sided 95% exact binomial confidence intervals will be determined including the recommended dose group (dose escalation cohort + Phase 2 cohort).

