**Efficacy Analyses**

Progression-free survival and duration of response will be listed for all subjects by dose level and schedule. Overall response rate and clinical benefit rate will be estimated for all subjects treated at the RP3D along with the associated 95% exact binomial confidence intervals (CIs).

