### 14.5.2 EFFICACY ANALYSES

Overall response rate is defined as the proportion of subjects with a best response of sCR, CR, VGPR, or PR as determined by investigator according to the IMWG-URC.

Clinical benefit rate is defined as the proportion of subjects with a best response of PR or better according to IMWG-URC or a best response of MR according to the EBMT criteria, as determined by the investigator. A point estimate and 95% exact binomial confidence interval (CI) will be calculated for both ORR and CBR for all subjects treated at the RP3D (during dose escalation and expansion for each schedule). A descriptive summary of ORR and responses will also be provided by dose cohort.

Progression-free survival and **duration of response (DOR)** will be listed for all subjects in the efficacy population by dose cohort level and schedule.

Approved

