7 STATISTICAL METHODS

7.1 General Considerations

This statistical analysis plan is being generated prior to locking the study database. It specifies the main efficacy and safety analyses to be performed.

All statistical summaries and analyses will be performed in SAS[®] version 9.3 or higher (SAS Institute Inc., Cary, NC, USA) on a PC platform.

In general, summaries of all data will be presented by schedule and dose groups, defined as initial dose level cohort for phase 1 and recommended dose cohort for phase 2. In addition, some summaries will include the combined recommended dose cohort from phase 1 and 2 and total cohorts (all subjects by schedule).

Summary statistics will be provided for selected endpoints. For continuous variables, the number of subjects with non-missing data (n), mean, standard deviation, median, minimum, and maximum will be presented. For discrete data, the frequency and percent distribution will be presented. Unless otherwise indicated, percentages will be calculated based upon the number of subjects in the Safety Population in each dose group as the denominator.

Confidence intervals, when presented, will be constructed at the 95% level. For binomial variables, exact distribution methods will be employed. The distribution of time-to-event endpoints will be summarized by Kaplan-Meier method. Quartiles including median will be estimated by Kaplan-Meier method along with their 95% confidence intervals.

Individual subject data recorded on the electronic case report forms (eCRFs) and any derived data will be presented by dose cohort and subject in data listings.

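### SAP 7.5 drops the protocol's CBR analysis without recording it, and SAP 7.5.1 sets an unexplained 1-sided ORR interval beside a 2-sided one

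*SAP*

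**What the plan says.** **Protocol.** Section 14.5.2 states: "A point estimate and 95% exact binomial confidence interval (CI) will be calculated for both ORR and CBR". The population is all subjects treated at the RP3D, "during dose escalation and expansion for each schedule". The synopsis repeats the plan for both rates, "along with the associated 95% exact binomial confidence intervals (CIs". Neither place says 1-sided or 2-sided.

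**SAP on CBR.** CBR is a secondary objective (2.3.2) and a secondary endpoint (3.2). Section 7.5 has two subsections, 7.5.1 for ORR and 7.5.2 for duration of response, and the SAP's table of contents lists the same two. No section plans a CBR estimate or interval. Section 1 undertakes that departures from the protocol's planned analyses will be identified in the SAP itself; none is recorded for CBR.

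**SAP on ORR.** Section 7.5.1 plans an ORR estimate and "its 1-sided 95% exact binomial confidence interval for each of the recommended dose groups will be determined". The next sentence adds that the "associated 2-sided 95% exact binomial confidence intervals will be determined including the recommended dose group (dose escalation cohort + Phase 2 cohort"). Section 7.1 sets the general rule, "Confidence intervals, when presented, will be constructed at the 95% level", with exact methods for binomial variables. Section 7.5.2 uses 2-sided 95% intervals for duration of response.

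**The concern.** The CBR gap is the more important part. A secondary endpoint for which the protocol specifies an estimate and an interval has no analysis in the document that programmers will follow. A reader of the abbreviated report could not tell whether CBR was dropped on purpose or overlooked.

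The ORR part is one of comparability. Two neighbouring ORR estimates would carry intervals with different tail areas: 5% in one tail for each recommended-dose group, and 2.5% in each tail for the combined group. The plan contains no null response rate or hypothesis test that would call for a one-sided bound, and the SAP does not say whether the bound is a lower or an upper one, so two programmers could produce different output from the same sentence.

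**Working it through.** **1. The plan's own ORR figure.** SAP 2.4 and protocol 14.7 give about 94% for at least 7 responses among 26 subjects (6 from escalation + 20 from expansion) if the true ORR is 40%. The exact binomial tail is P(X ≥ 7 | n = 26, p = 0.40) = 0.9441, so the figure reproduces. It is a tail probability for the combined 26 and does not depend on any confidence interval. It therefore neither explains nor is affected by the 1-sided choice.

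**2. Coverage of the two rates, side by side.**

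| Rate | Protocol 14.5.2 | SAP objective/endpoint | SAP 7.5 analysis |
|---|---|---|---|
| ORR | Estimate + 95% exact CI, RP3D subjects by schedule | Yes (2.3.2, 3.2) | Yes: 1-sided per recommended-dose group, 2-sided combined |
| CBR | Same as ORR | Yes (2.3.2, 3.2) | None |

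SAP 7.1 does not fill the CBR cell. It fixes the level and method of an interval if one is presented, and does not commit to presenting one. Nor is this an effect of protocol version. The SAP was written against Amendment 2, and the change table for that amendment shows the same 14.5.2 requirement for both rates.

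**3. Which group gets the 1-sided interval.** SAP 7.1 treats the phase 2 recommended-dose cohort as a dose group of its own, with the combined cohort as an addition. The 1-sided interval therefore most likely applies to the expansion cohort alone, planned at a minimum of 20 subjects per schedule expanded.

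**4. Size of the difference.** Exact (Clopper-Pearson) limits for x responders of n:
- lower = Beta quantile at a, with parameters (x, n − x + 1)
- upper = Beta quantile at 1 − a, with parameters (x + 1, n − x)
- a = 0.05 for a 1-sided 95% bound; a = 0.025 for each limit of a 2-sided 95% interval

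The documents give no results. The counts below, and n = 20 itself, are assumptions.

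| x/n | 1-sided, if lower | 1-sided, if upper | 2-sided 95% | Gap in lower limit |
|---|---|---|---|---|
| 6/20 (30%) | 14.0–100% | 0–50.8% | 11.9–54.3% | 14.0 − 11.9 = 2.1 |
| 8/20 (40%) | 21.7–100% | 0–60.6% | 19.1–63.9% | 21.7 − 19.1 = 2.6 |
| 10/20 (50%) | 30.2–100% | 0–69.8% | 27.2–72.8% | 30.2 − 27.2 = 3.0 |

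For the combined 26, where the SAP already plans the 2-sided interval, 7/26 gives 11.6–47.8% and 10/26 gives 20.2–59.4%. Both bounds are reported there.

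**The case against.** The strongest reply concerns ORR. A reader of the first sentence of 7.5.1 alone might infer that the SAP has replaced the protocol's interval with a one-sided one and that no upper bound for ORR will be reported. The documents do not support that. The next sentence, though loosely worded, plans a 2-sided 95% exact interval for the escalation plus Phase 2 subjects at the recommended dose, which is the population that protocol 14.5.2 names. The 1-sided interval is best read as an addition for a subset for which the protocol plans no interval, so for ORR no protocol analysis has been removed.

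A reader might also infer that the 1-sided bound makes activity look better than it is. That goes too far as well. A 1-sided 95% exact bound has the coverage it claims and is labelled 1-sided. The 2 to 3 point gap arises only if a lower bound is meant, and it is small against a 2-sided interval about 45 points wide (63.9 − 19.1 = 44.8 at 8/20). No decision rule uses the bound, ORR is a secondary endpoint, and SAP 2.1 gives other reasons for cancelling Part 2.

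Those points stand, and they reduce the ORR part to a matter of clarity and comparability. They do not remove it. Expansion subjects differ by design from escalation subjects: protocol 6.1 requires adequate alkylator therapy in expansion only, and 6.2 excludes any prior pomalidomide there but not in escalation. Readers have good reason to set the two estimates side by side. For CBR, the best defence is that an abbreviated report may carry fewer analyses. That may be so, but SAP Section 1 requires such a change to be written down, and it is not.

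**Conclusion.** The point holds in two parts of unequal weight. First, the SAP omits a protocol-specified secondary analysis (CBR estimate and 95% exact interval at the RP3D by schedule) while keeping CBR as an objective and endpoint, and does not record the change. This follows from the text and needs no assumption. Second, the 1-sided ORR interval has no stated direction or reason and cannot be compared with the 2-sided interval beside it. The size given for this second part, about 2 to 3 percentage points in the lower limit and no informative upper limit for that group, assumes that a lower bound is intended, that n = 20, and illustrative counts of 6, 8 and 10. The protocol's own ORR interval survives with both bounds, and the 94% statement is unaffected. Reading a 95% CI in the protocol as 2-sided is the usual convention, but the protocol does not say so. The change should be made, mainly because of CBR.

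**What to change.** In SAP 7.5.1, change 1-sided to 2-sided, so that every ORR interval is a 2-sided 95% exact (Clopper-Pearson) interval. Add a CBR subsection to SAP 7.5 with a point estimate and 2-sided 95% exact interval, at minimum for all subjects treated at the RP3D (escalation plus expansion) by schedule, and preferably for the same groups as ORR. If the sponsor prefers to keep the 1-sided interval or to leave CBR out, the SAP should state the direction and purpose of the bound, and record the CBR omission with its reason as Section 1 requires.

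The cost is one word and one extra table, built from response assessments the protocol already plans to collect. If a lower bound was intended, the reported lower limit for the recommended-dose group would fall by about 2 to 3 points under the assumed counts.

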7.5.2 Duration of Response

Duration of response (DOR) will be calculated for subjects who achieve a sCR, CR, nCR, VGPR, or PR. For such subjects, the duration of overall response is defined as the time from first evidence of PR or better to disease progression or death due to any cause.

$$DOR = \text{Earliest date of disease progression, death, or censoring} - \text{Date of first observation of PR or better before confirmation} + 1 \text{ and expressed in months}$$

Duration of response will be right-censored for subjects who at least achieve a PR based on the censoring conventions defined previously for PFS. Analysis of DOR will be performed using the Kaplan–Meier method. Medians and other quartiles for DOR will be estimated in addition to the corresponding 2-sided 95% confidence intervals.

7.6 Safety Analysis

All safety analyses will be based on the Safety population.

7.6.1 Adverse Events

Each reported AE term will be mapped to a preferred term (PT) and a system organ class (SOC) using the Medical Dictionary for Regulatory Activities (MedDRA).

Treatment-emergent adverse events (TEAEs) are defined as AEs that start on or after the first day of study treatment and within 30 days of the last day of study treatment. An AE that is present before the first administration of study treatment and subsequently worsens in severity during treatment is also considered to be treatment-emergent.

Adverse events will be summarized based on the number (%) of subjects experiencing events by MedDRA system organ class and preferred term. The denominator for the

percentage will be based on the number of subjects at in the Safety Population (i.e., those that received at least one dose of study drug).

A subject reporting the same AE more than once will be counted only once when calculating 1) within a given system organ class, and 2) within a given system organ class and preferred term combination. For such cases, the maximum National Cancer Institute (NCI; US) - Common Terminology Criteria for Adverse Events toxicity grade and strongest causal relationship to study treatment for the event will be used in the incidence calculations. AEs will also be summarized by severity and by relationship to study drug.

An overall summary of TEAEs will summarize the number (%) of subjects

- with at least one TEAE
- with at least one treatment-related TEAE, defined as related to OPZ or DEX
- with at least one grade 3 or higher TEAE
- with at least one treatment-related grade 3 or higher TEAE, either OPZ or DEX
- with at least one serious AE
- with TEAE leading to discontinuation of study drug, either OPZ or DEX
- with TEAE leading to discontinuation of OPZ
- who died within 30 days of last dose of study drug

Summaries of the following TEAEs will be provided by SOC and/ or PT unless otherwise noted:

- all TEAEs
- all TEAs (PT)
- TEAEs by maximum severity
- TEAEs grade 3 or higher (PT)
- treatment-related adverse events (OPZ, POM, DEX, and study drug)

- serious TEAEs
- TEAEs that led to permanent discontinuation of study drug (OPZ, POM, DEX and study treatment)

Summaries that are displayed by system organ class and preferred terms will be ordered by descending order of incidence of system organ class and preferred term within each system organ class for the total group. Summaries of TEAEs, treatment-related AEs will also be provided by descending order of incidence of preferred terms in the total group.

All AEs, including TEAEs, will be included in listings by subject.

Listings of AEs determined to be DLTs during the first cycle of Phase 1, serious AEs, and AEs leading to discontinuation of study drug will be provided.

A summary of the number of deaths and the cause of death, classified by deaths within 30 days of last dose of study drug and deaths more than 30 days after the last dose, will be provided.

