## 13 ADVERSE EVENTS AND SERIOUS ADVERSE EVENTS

### 13.1 ADVERSE EVENT REPORTING

#### 13.1.1 DEFINITIONS

An AE is any untoward medical occurrence in a study subject administered an investigational product(s) regardless of the causal relationship with treatment.

Approved

An AE, therefore, can be any unfavorable and unintended sign (including laboratory finding), symptom, or disease temporally associated with participation in an investigational study, whether or not considered drug-related. In addition to new events, any increase in the severity or frequency of a preexisting condition that occurs after the subject signs the informed consent form (ICF) for participation is considered an AE. This includes any side effect, injury, toxicity, or sensitivity reaction. All reported AEs will be coded using the current version of Medical Dictionary for Regulatory Activities (MedDRA).

Whenever possible, the NCI-CTCAE Version 4.03 should be used to describe the event and for assessing the severity of AEs. For AEs not adequately addressed in the NCI-CTCAE Version 4.03, [Table 17](#) below should be used.

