### 13.3 ADVERSE EVENTS REPORTING PROCEDURES

#### 13.3.1 GENERAL

All AEs (eg, any new event or worsening in severity or frequency of a preexisting condition or laboratory finding) with an onset date after the subject signs the informed consent for participation in the clinical trial must be promptly documented on the AE eCRF via the electronic data capture (EDC) system. Details of the event must include severity, relationship to study drug(s), duration, action taken, and outcome. Whenever possible, reporting a specific diagnosis is preferred when reporting AEs in the AE eCRF rather than reporting individual signs and symptoms.

All AEs will be collected from the time the subject signs informed consent through 30 days after receiving the last dose of study drug or before start of subsequent anticancer treatment (whichever occurs first). If initiation of new anticancer therapy occurs following the last dose of study drug(s), the date of new anticancer therapy will be recorded on the appropriate eCRF. In addition, the investigator should report any AEs that may occur after this time period that are assessed to have a reasonable possibility of being associated with study drug. If the subject is randomized but discontinues participation in the study prior to receiving study drug, AEs must be reported through the End of Study Treatment visit.

All AE severity changes will be recorded on the AE case report form (CRF) as separate events. All AEs that are considered related to study drug and all SAEs regardless of relationship to study drug must be followed to resolution or to stabilization if improvement is not expected. Adverse events that completely resolve and then recur should be recorded as a new AE. For subjects who complete the End of Study Treatment visit less than 30 days following the last dose of study drug, a follow-up of ongoing AEs should be attempted by telephone and documented in the subject's source file. Adverse events continuing at 30 days after the last dose of study treatment should have a comment in the source file by the investigator that the event has stabilized or is not expected to improve.

Approved

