7.7 Handling of Dropouts or Missing Data

The handling of dropouts and missing disease status assessments for the efficacy variables is described in their definitions.

Missing or partially missing dates will not be imputed at data level. However, assumptions for missing or partially missing dates for important variables will be made to allow inclusion of appropriate data records in the analyses.

If a medication date or time is missing or partially missing, so it cannot be determined whether it was taken prior or concomitantly, it will be considered as a prior, concomitant, and a post-treatment medication.

If the partial AE onset date information does not indicate whether the AE started prior to treatment or after the TEAE period, the AE will be classified as TEAEs.

If the start day of subsequent anti-cancer therapy is missing, it will be assumed to be the first day of the month.

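### SAP 7.6.1 can count an AE that arose before first dose and improved on treatment as treatment-emergent, because severity changes are separate events and no rule links them or compares grades

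*SAP*

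**What the plan says.** **Collection.** Protocol 13.3.1: "All AEs will be collected from the time the subject signs informed consent through 30 days after receiving the last dose of study drug" (or until new anticancer treatment, if earlier). Protocol Section 7 allows screening up to 28 days before first dose, so AEs that start before treatment are in the database. Protocol 13.1.1 assigns anything with onset before consent to medical history, but counts a post-consent increase in its severity or frequency as an AE.

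**Recording.** Protocol 13.3.1: "All AE severity changes will be recorded on the AE case report form (CRF) as separate events". Nothing limits this to worsening.

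**Classification.** SAP 7.6.1 calls treatment-emergent those "AEs that start on or after the first day of study treatment and within 30 days of the last day of study treatment". The next sentence adds that an AE present before first dose that "subsequently worsens in severity during treatment is also considered to be treatment-emergent".

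**Counting.** SAP 7.6.1: "A subject reporting the same AE more than once will be counted only once when calculating"; this applies within a system organ class and within a preferred term. The maximum grade and the "strongest causal relationship to study treatment for the event will be used in the incidence calculations".

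**Missing dates.** SAP 7.7 addresses only incomplete onset dates: "If the partial AE onset date information does not indicate whether the AE started prior to treatment or after the TEAE period", the AE is classed as treatment-emergent.

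No section of the SAP links the records of one episode or compares a post-dose record with the grade before dosing.

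**The concern.** The recording convention and the TEAE definition were not aligned. Once each grade has its own record, a test on start date alone accepts any grade change that occurs after dosing begins, including a change for the better. The worsening sentence does not close the gap: it adds a second way in and puts no limit on the first.

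Adverse events are a primary endpoint (Protocol 14.1.1, SAP 3.1), and safety and tolerability are among the criteria for choosing the RP3D (Protocol 5.1.5 and 14.7). The tables are shown by schedule and dose group (SAP 7.1), so groups are small and one misclassified subject is visible in a preferred-term row. The error runs in one direction only: it adds TEAEs and never removes them.

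**Working it through.** The plan states no figure on this point, so there is none to reproduce. The check applies the written rule to invented records, then works out what one misclassified subject is worth.

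**Step 1. Apply the rule as written.** Assumed records, one per severity change, each starting on the date of change; last dose on Day 84, so the TEAE window runs from Day 1 to Day 84 + 30 = Day 114.

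- Subject A: nausea, Grade 3 from Day -5, Grade 1 from Day 4 (improves).
- Subject B: fatigue, Grade 1 from Day -5, Grade 2 from Day 4 (worsens).
- Subject C: anemia, Grade 2 from Day -5, unchanged.

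Start-date rule (1 ≤ start day ≤ 114): A's second record and B's second record qualify. Result: A and B have TEAEs.

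Linked rule (same window, and grade above the pre-dose grade): A has 1 > 3, false; B has 2 > 1, true. Result: only B has a TEAE.

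The two rules differ only on A, whose event did nothing but improve.

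**Step 2. Size per affected subject.** The increment to a preferred-term incidence is 100/n percentage points.

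- Escalation cohort of 3 to 6 (Protocol 5.1): 100/3 = 33.3 and 100/6 = 16.7.
- Recommended-dose group of 26, being 6 from escalation + 20 from expansion (Protocol 14.7, SAP 2.4): 100/26 = 3.8.
- All 82 planned subjects: 100/82 = 1.2.

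**Step 3. What limits the effect.**

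- Exposed group: only AEs that begin or worsen between consent and first dose and are still present at first dose. A condition with onset before consent that merely improves has no AE record.
- Counting: subjects count once per preferred term. A diarrhea that falls from Grade 3 to 2 to 1 on treatment makes two qualifying records but adds at most one subject, and adds none if that subject has another TEAE in the same term.
- Grade: with the maximum taken over the records flagged as TEAEs, the subject enters at the improved grade. The Grade 3 or higher table changes only for a step such as Grade 4 to Grade 3.
- Dose decisions: DLTs are drug-related events reviewed by the CSRC (Protocol 5.1.3 and 10.5) and do not depend on the TEAE flag.

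**The case against.** The best counter-argument is that the SAP classifies AEs, not CRF records. Its second sentence treats an AE present before dosing, and later worse, as one continuing AE. On that reading an improving AE started before dosing, did not worsen, and meets neither sentence. Protocol 13.1.1 supports this, since for preexisting conditions it names only increases as AEs. In addition, no text says that the separate record takes a new onset date, and Protocol 13.3.1 uses different words for an event that resolves and recurs, which becomes a new AE.

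Part of this stands. The intent is reasonably clear, and the onset date on the date of change is an inference. But the one-continuing-AE reading sits badly with a protocol that makes each severity change a separate event. It also needs those separate entries to be joined again before the flag is set, and the SAP gives no rule for that. If each change is its own event, the worsening sentence is largely redundant, which suggests the SAP was not written with the CRF convention in view. Either reading leads to the same missing step.

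It is also fair to say that TEAE tables are descriptive and all-cause, that treatment-related events are summarized separately, and that all AEs are listed by subject. These limit the harm but do not correct the incidence.

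The SAP cites Amendment 2 while the protocol text supplied is Amendment 3. The Amendment 3 summary of changes shows no change to the recording sentence.

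**Conclusion.** The gap is real and worth closing. As written, and if the separate record starts on the date of change, an AE that arises or worsens between consent and first dose and then improves on treatment is counted as a TEAE. Each such subject with no other TEAE in that preferred term adds 3.8 points at n = 26, or 17 to 33 points in a cohort of 3 to 6. The number of such subjects is not in the documents.

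A reader might infer more than this, and the documents do not support it:

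- *That improving myeloma symptoms in general are reported as toxicity.* Symptoms with onset before consent are medical history and create no record when they ease.
- *That a stated share of subjects is affected.* If 10 to 30% had an AE that began before dosing and was ongoing on Day 1, and half of those improved, 26 × 0.10 × 0.5 = 1.3 to 26 × 0.30 × 0.5 = 3.9 subjects would carry such a record. Both inputs are assumptions without a source here. For any one preferred term the range is an upper bound, because the subjects would spread across terms and some would have a genuine TEAE in the same term.
- *That severe-event rates or dose decisions are distorted.* The Grade 3 or higher table changes only in cases such as Grade 4 to 3, and DLT and MTD determination is separate.

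**What to change.** Add to SAP 7.6.1: records of the same AE episode in a subject are linked before the TEAE flag is set; a record starting on or after first dose that continues an AE present before first dose is treatment-emergent only if its grade exceeds the pre-dose grade.

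State the reference grade. The last grade before first dose agrees with the baseline definition in SAP 5.3; the worst pre-dose grade is the alternative, and the choice can matter. With Grade 3 on Day -5, Grade 1 on Day -1 and Grade 2 on Day 4, the first reference gives a TEAE (2 > 1) and the second does not (2 > 3 is false).

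Cost: one rule in the SAP and a small linking step in the AE derivation. The documents show no variable that ties records together, so the rule should say how it is done, for example by subject, preferred term and contiguous dates. No new data should be needed if the CRF holds those dates. The sponsor can confirm from the CRF completion guideline that a severity-change record takes the date of change as its start, and can count the affected records directly. A change after SAP finalization would be noted with its reason in the abbreviated report, as SAP Section 1 already requires.
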